4 SELECTION AND WITHDRAWAL OF PATIENTS

4.1 Inclusion Criteria

Patients who meet all of the following criteria will be eligible to participate in the study:

1. Informed consent form (ICF) signed voluntarily before any study-related procedure is performed, indicating that the patient understands the purpose of, and procedures required for, the study and is willing to participate in the study;
2. Males and females ≥ 18 years of age at screening;
3. ECOG PS of 0 to 1 (see [Appendix C](#));
4. HER2-positive locally advanced or metastatic breast cancer refractory to standard cancer treatment or HER2-positive locally advanced or metastatic gastric or GEJ cancer, refractory to standard cancer treatment;
5. Patients should have a minimum of 1 measurable lesion as defined by RECIST version 1.1 or a minimum of 1 measurable lesion as defined by RANO-BM within 4 weeks of the first dose of the study drug (Day 1). The lesion has to be a new lesion or progression of an existing lesion under the current therapy;
6. Any previous anti-HER2 treatment for advanced or metastatic disease is allowed. Patients with breast cancer should have had at least 2 previous systemic anticancer treatments for recurrent, locally advanced or metastatic cancer. Patients with gastric cancer or GEJ cancer should have had at least 1 previous anti-HER2 treatment;
7. Life expectancy >6 months;
8. Adequate organ function, determined by the following laboratory tests at screening:
 - Adequate kidney function with an eGFR of >59 mL/minute calculated using the Chronic Kidney Disease Epidemiology Collaboration equation;¹²
 - Adequate hepatic function defined as an ALT and AST $<2.5 \times$ ULN, or $<5 \times$ ULN in patients with liver metastases, and total bilirubin $<2 \times$ ULN;
 - Neutrophil count >1500 cells/mm³ without growth factor support (14 days after last pegylated granulocyte colony-stimulating factor or 7 days after regular granulocyte colony-stimulating factor);
 - Platelet count $>100,000$ cells/mm³ without platelet transfusion in the last 2 weeks;
 - Hemoglobin >9.0 g/dL without blood transfusion in the last 2 weeks; and
 - Adequate coagulation defined as an international normalized ratio (INR) ≤ 1.5 and activated partial thromboplastin time $<1.5 \times$ the upper limit of the institutional normal range;
9. Baseline left ventricular ejection fraction (LVEF) $\geq 50\%$ as measured by echocardiography or multigated acquisition scan;

10. Absence of any psychological, family, sociological, or geographical circumstance that could potentially represent an obstacle to compliance with the study protocol and the follow-up schedule, as determined by the Investigator. These circumstances will be discussed with the patient before enrollment in the study; and
11. Female patients of childbearing potential (ie, ovulating, premenopausal, and not surgically sterile) must have a negative pregnancy test at screening and prior to study drug administration. Patients and their partners of childbearing potential must be willing to use 2 methods of contraception, 1 of which must be a barrier method, for the duration of the study and until 6 months after study drug administration. Medically acceptable barrier methods include condom with spermicide or diaphragm with spermicide. Medically acceptable non-barrier contraceptive methods include intrauterine devices or hormonal contraceptives (oral, implant, injection, ring, or patch).

4.2 Exclusion Criteria

Patients who meet any of the following criteria will be excluded from participation in the study:

1. Presence of frank leptomeningeal disease as a unique central nervous system feature or in association with brain parenchymal measurable lesion(s);
2. Symptomatic brain metastases;

Note: Patients with asymptomatic treated and untreated brain metastases are eligible.

3. Previous local therapy for brain metastases, such as neurosurgery, stereotactic radiotherapy, or whole brain radiotherapy, administered within 6 weeks prior to administration of CAM-H2;

Note: Previous therapy for brain metastases administered at least 6 weeks prior to CAM-H2 administration will be allowed.

4. For patients with brain metastases, any increase in corticosteroid dose during the 4 weeks prior to the first administration of CAM-H2;

Note: Corticosteroid treatment in a stable dose or decreasing dose for at least 4 weeks prior to the first administration of CAM-H2 is allowed.

5. Uncontrolled intercurrent illness including, but not limited to, ongoing or active infection requiring parenteral antibiotics or psychiatric illness/social situations that would limit compliance with study requirements;

6. Uncontrolled thyroid disease, defined as free triiodothyronine (T3) and free thyroxine (T4) $>3 \times$ ULN at screening;

7. Uncontrolled diabetes defined as a fasting serum glucose $>2 \times$ ULN or glycated hemoglobin levels $>8.5\%$ at screening;

8. Gastrointestinal (GI) tract disease resulting in an inability to take oral medication, malabsorption syndrome, a requirement for IV alimentation, prior surgical procedures affecting absorption, or uncontrolled inflammatory GI disease (eg, Crohn's, ulcerative colitis);

9. Current active hepatic or biliary disease (exception of patients with Gilbert's syndrome, asymptomatic gallstones, liver metastases, or stable chronic liver disease per Investigator assessment);

10. Ongoing peripheral neuropathy of Grade >2 according to the CTCAE version 5.0;
11. Severe and/or uncontrolled medical conditions or other conditions that could affect participation in the study such as:
 - Symptomatic congestive heart failure of New York Heart Association Class III or IV;
 - Unstable angina pectoris, symptomatic congestive heart failure, myocardial infarction within 6 months of start of study drug, serious uncontrolled cardiac arrhythmia, or any other clinically significant cardiac disease; or
 - Liver disease, including cirrhosis and severe hepatic impairment;
12. Active (acute or chronic) or uncontrolled severe infections;
13. Known history of HIV, hepatitis B, or active hepatitis C virus at screening;
14. Prior investigational anticancer therapy within 4 weeks prior to the first administration of CAM-H2;
15. Patients who have had a major surgery or significant traumatic injury within 4 weeks prior to the first administration of CAM-H2, who have not recovered from side effects of any major surgery (defined as requiring general anesthesia), or have a major surgery planned during the course of the study;
16. Other malignancies within the past 3 years except for adequately treated carcinoma of the cervix or basal or squamous cell carcinomas of the skin or stage I uterine cancer;
17. Radiation therapy for metastatic disease foci outside the brain, administered within 3 weeks prior to the first administration of CAM-H2;
18. Known hypersensitivity to any of the study drugs (including inactive ingredients) including iodine allergy;
19. History of significant comorbidities that, in the Investigator's judgement, may interfere with study conduct, response assessment, or informed consent;
20. Unable or unwilling to complete the study procedures;
21. Patients that cannot be hospitalized in a radionuclide therapy room;
22. Patients with urinary incontinence;
23. Patients that are unable to comply with thyroid protective pre-medication;
24. Patients in whom bladder catheterization cannot be performed, or in patients who are unwilling to be catheterized if necessary;
25. Patients with contraindications for undergoing MRI or CT, including for receiving contrast agents; or
26. Patient is the Investigator or sub-Investigator, research assistant, pharmacist, study coordinator, or other staff or relative thereof, who is directly involved in the conduct of the study.

4.3 Withdrawal Criteria

Participation of a patient in this clinical study may be discontinued for any of the following reasons:

- Withdrawal of consent or a request to discontinue from the study for any reason;
- Occurrence of any medical condition or circumstance that exposes the patient to substantial risk and/or does not allow the patient to adhere to the requirements of the protocol;
- Occurrence of any SAE, clinically significant AE, severe laboratory abnormality, intercurrent illness, or other medical condition which indicates to the Investigator that continued participation is not in the best interest of the patient;
- Pregnancy;
- Requirement of prohibited concomitant medication;
- Patient failure to comply with protocol requirements or study-related procedures; or
- Termination of the study by the Sponsor or the regulatory authority.

If a patient withdraws prematurely from the study due to the above criteria or any other reason, study staff should make every effort to complete the full panel of assessments scheduled for the EOT Visit (Visit 11 in Cycle 1 or Visit 20 in Cycle 2 of either the dose escalation or dose expansion phases). The reason for patient withdrawal must be documented in the electronic case report form (eCRF).

In the case of patients lost to follow-up, a minimum of 3 attempts to contact the patient (ie, 2 phone calls and 1 certified letter) must be made and documented in the patient's eCRF.

Withdrawn patients may be replaced to ensure adequate numbers of evaluable patients at the discretion of the Sponsor with agreement from the Investigator.

5 STUDY TREATMENTS

5.1 Dose Groups

The planned dose levels of CAM-H2 to be used in the dose escalation phase are demonstrated in Table 3. All patients will receive at least 1 cycle of CAM-H2. During the dose escalation phase, patients with CB may receive up to 4 cycles of CAM-H2, as long as the cumulative kidney dose remains <23 Gy (based on the dosimetry results during Cycle 1).

The dose escalation phase of the study will be an open-label 3 + 3 design, where at least 3 patients are treated at each dose level. Dose escalation will be done via increases of the nominal activity of CAM-H2 in cohorts of 3 to 6 patients.

Staggered dosing will be applied for all cohorts during dose escalation. The first dose of the first patient of a cohort will be administered at least 2 weeks before the first dose of the next 2 patients (sentinel dosing). Dose levels per cycle will start at 2×1.85 GBq (2×50 mCi) for cohort 1. A maximum dose of 2×7.40 GBq (2×200 mCi) is planned for cohort 4 if neither the MTD nor RDP2 is reached at cohort 3.

Table 3. Dose Escalation Schedule for Each CAM-H2 Cycle

Dose Level	Activity of CAM-H2 (GBq) [1]	Activity of CAM-H2 (mCi) [1]
Level 1 (starting activity)	2×1.85	2×50
Level 2	2×3.7	2×100
Level 3	2×5.55	2×150
Level 4 [2]	2×7.4	2×200

1. Doses will be given 4 weeks apart. All patients will receive at least 1 cycle of CAM-H2.
2. Level 4 dosing will be optional, depending on overall safety, tolerability, and dosimetry.

In the dose expansion phase of the study, the patients will be given the RDP2 determined in the dose escalation phase. Similar to the dose escalation phase, all patients will receive at least 1 cycle of CAM-H2. During the dose expansion phase, patients with CB may receive up to 2 cycles of CAM-H2, as long as the cumulative kidney dose remains <23 Gy (based on the dosimetry results during Cycle 1 of dose escalation).

5.2 Drug Supplies

5.2.1 Formulation and Packaging

CAM-H2 contains the radioactive $[^{131}\text{I}]$ -GMIB-2Rs15d. Dosing of CAM-H2 will be done via dose escalation as described in Section 5.1 for the dose escalation phase. Once the RDP2 is determined, that RDP2 dose will be given in the dose expansion phase.

CAM-H2 will be provided as a clear, sterile solution for IV administration. The solution is provided in a 30 mL round glass vial with a rubber stopper and aluminum seal. The vial is then covered with a 2-piece lead pig, closed with 2 metal screws, and wrapped in protective bubble wrap. See the Investigator's Brochure or Investigational Medicinal Product manual for more information.

CAM-H2 will be manufactured and prepared for administration at the manufacturing unit for direct supply to the site. The shipment from the manufacturing unit to the site will be within a secondary shielding container and will be temperature-controlled.

Both primary and secondary packaging will be labeled in accordance with local regulations.

5.2.2 Study Drug Administration

Two plastic IV catheters should be inserted into the patient's peripheral veins using 2 different lines. The catheters should be connected to the infusion set: 1 for the study drug and 1 for the amino acid infusion. If, for practical reasons, 2 peripheral lines are not possible, the study drug and the amino acid infusion can be administered using a central line (dual lumen catheter) or a single peripheral catheter. In case of a single peripheral catheter, the amino acid infusion needs to be temporarily halted during the study CAM-H2 infusion and resumed once the catheter has been flushed. In any case, separate lines are to be prepared to minimize the mixing of substances. If a patient has a port-a-cath (or equivalent) system, then this entry port can be used for the amino acid (and saline) infusion.

The study drug will be administered at the sites by qualified study personnel. CAM-H2 is injected via a slow IV infusion. The study drug will be administered using a shielded infusion device over approximately 3 to 30 minutes, depending on the volume to be injected. The study drug can be infused at a rate compatible with the radioprotection guidance for site staff and in a time adequate to ensure patient safety. The time can be reduced to 1 minute if deemed feasible by the Investigator, depending on the total volume to be infused.

5.2.2.1 Radioprotection rules

CAM-H2 should always be infused through an IV catheter placed exclusively for its infusion. The adequate position of the catheter should be checked before and during infusion.

Patients will be admitted to a radioactive unit for hospitalization during each IV administration for a total of 48 hours. This hospitalization can be shortened if ¹³¹I decay and the patient's clearance allow discharge according to the applicable local regulations on radioactive compound exposure. Each patient treated with CAM-H2 should be kept away from others during the administration and up to reaching the radiation emission limits stipulated by applicable laws. The nuclear medicine physician should determine when the patient can leave the controlled area of the hospital (ie, when the radiation exposure to third parties does not exceed regulatory thresholds).

The patient should be encouraged to urinate as much as possible after study drug administration. Patients should be instructed to drink substantial quantities of water (ie, 1 glass every hour) on the day of infusion and the day after infusion to facilitate elimination. The patient should also be encouraged to defecate every day and to use laxatives if needed. Urine and feces should be disposed according to the national regulations.

As long as the patient's skin is not contaminated, such as from the leakage of the infusion system or because of urinary incontinence, radioactivity contamination is not expected on the skin or vomited mass. However, it is recommended that when conducting standard of care procedures or examinations with medical devices or other instruments which contact the skin (eg, ECG), basic protection measures are observed, including wearing gloves, installing the material or electrode before the start of radiopharmaceutical infusion, changing the material or electrode after measurement, and monitoring the radioactivity of equipment after use.

Before the patient is released, the nuclear physician should explain the necessary radioprotection rules of interacting with family members and third parties and the general precautions the patient must follow during daily activities after treatment to minimize radiation exposure to others. A leaflet containing this information, which is in accordance with the Practice Recommendations of the American Thyroid Association,¹³ will be distributed (see [Appendix F](#)).

Close contact with other people should be restricted during the 7 days following an administration of the study drug. For children and pregnant women, patient contact should be limited to less than 15 minutes daily while keeping a distance of at least 1 meter. Patients should sleep in a separate bedroom from other individuals for at least 7 days, or at least 15 days in the case of children or pregnant partners.

Recommended measures in case of extravasation

In the case of extravasation of study drug, disposable waterproof gloves should be worn, the infusion of the study drug must be immediately ceased, and the administration device (eg, catheter) must be removed. The nuclear medicine physician and the radiopharmacist should be informed.

All the administration device materials should be kept in order to measure the activity actually administered and eventually the absorbed dose. The extravasation area should be delimited with an indelible pen and a picture should be taken if possible. It is also recommended to record the time of extravasation and the estimated volume extravasated. To continue study drug infusion, it is mandatory to use a new catheter, possibly placing it in a contralateral venous access.

No additional medicinal product can be administered to the same side where the extravasation occurred. In order to accelerate medicinal product dispersion and to prevent its stagnation in tissue, it is recommended to increase blood flow by elevating the affected arm. Depending on the case, the aspiration of extravasation fluid, a flush injection of sodium chloride 9 mg/mL (0.9%) solution, or the application of warm compresses or a heating pad to the infusion site to accelerate vasodilation should be considered.

Symptoms, especially inflammation and/or pain, should be treated. Depending on the situation, the nuclear medicine physician should inform the patient about the risks linked to extravasation injury and give advice about potential treatment and necessary follow-up requirements. The extravasation area must be monitored until the patient is discharged from the hospital. Depending upon its seriousness, this event should be declared as an adverse reaction.

5.2.3 Treatment Compliance

Study drug will be administered at the site by a qualified staff member. The exact times of study drug administration and the dose administered will be recorded in the eCRF.

Total activity administered will be equal to the activity in the vial before the infusion minus the activity remaining in the vial after the infusion. The measurements should be performed using a calibrated system. See the Pharmacy Manual for the exact procedure.

5.2.4 Storage and Accountability

CAM-H2 may be stored at room temperature but is also stable below $\leq -70^{\circ}\text{C}$. CAM-H2 has a shelf life of 144 hours after production. The vial should never be stored in an inverted orientation.

CAM-H2 will be stored in a secure area with access limited to authorized personnel. The site will perform an ongoing inventory of study drug on behalf of Precirix NV. The responsible staff at the site will keep an accurate inventory of study drug shipments received and the amount of study drug used per patient. A full reconciliation of study drug inventory will be performed at the end of the study and the results of the inventory recorded.

See the Pharmacy Manual for more information.

5.2.5 Ancillary Treatments to be Given With CAM-H2

5.2.5.1 Thyroid-blocking drugs

Acceptable thyroid-blocking drugs and their recommended doses are presented in Table 4. Patients will not always take the thyroid-blocking drugs on the same day that they are delivered. All patients will take potassium iodide 130 mg daily (or equivalent) starting 24 hours before study drug administration, 1 hour before study drug administration, and 24 and 48 hours after study drug administration as indicated. Depending on the site's standard operating procedures and local availability, this formulation can be adapted as per applicable guidance.

Confirmation of ingestion of thyroid-blocking drugs will be performed by directly asking the patient and by counting pills left in his/her medication bottle.

Table 4. Thyroid-Blocking Drugs

Compound	Formulation	Daily Dose
Potassium iodate	Capsule	170 mg
Potassium iodide	Capsule	130 mg
Lugol's 1%	Solution	1 drop/kg to a maximum of 40 drops (20 drops twice daily)
Potassium perchlorate	Capsule	400 mg

5.2.5.2 Anti-emetic, anti-histamine, and anti-pyretic premedication therapy

Anti-emetic, anti-histamine, and anti-pyretic premedication should be administered approximately 30 minutes prior to the start of the amino acid infusion during the study, according to the site's standard operating procedures.

Sites will administer ondansetron 8 mg IV (or equivalent), diphenhydramine 50 mg IV (or equivalent anti-histamine dose orally), and acetaminophen or paracetamol 500 to 1000 mg orally.

In the case of severe nausea or vomiting during the study drug or amino acid infusion, additional anti-emetic therapy can be initiated as per local procedures.

5.2.5.3 Saline infusion

Saline 0.9% infusion will be initiated 30 minutes prior to study drug administration and continued for up to 3 hours after, at a rate of 200 to 300 mL/hour.

5.2.5.4 Amino acid infusion

Administration of the amino acid solution should be initiated 30 minutes prior to study drug administration with an infusion rate of 250 to 500 mL/hour. Amino acid solution infusion should be continued for 3 hours after study drug administration. Rates lower than 320 mL/hour are not recommended for commercial solutions.

If needed, in case of poor venous access, a 3-way stopcock may be used for the amino acid infusion, the study drug, and saline. The dose of the amino acid solution should not be decreased if the dose of CAM-H2 is reduced.

The amino acid solution will be prepared as a compounded product, in compliance with the hospital's sterile medicinal product preparation good practices and according to the composition specified in [Table 5](#).

Table 5. Composition of the Standard Amino Acid Solution

Compound	Amount
Lysine	25 g
Arginine	25 g
Sodium chloride 9 mg/mL solution for injection	1 L

Alternatively, some commercially available amino acid solutions can be used if compliant with the specification described in Table 6.

Table 6. Specification of Commercially Available Amino Acid Solutions

Characteristic	Specification
Lysine content	Between 18 and 24 g
Arginine content	Between 18 and 24 g
Volume	1.5 to 2.2 L
Osmolarity	<1.050 mOsmol

Considering the high quantity of amino acids and the significant volume that commercially available solutions may require to meet the above specifications, the compounded solution is considered the medicinal product of choice, due to its lower total volume to be infused and lower osmolarity.

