1.3.2 Dosimetry Rationale

The proposed dose escalation of radioactivity is based on dosimetry extrapolations obtained in the dosimetry study in non-human primates using the study drug. The proposed dose escalation is described in [Section 5.1](#).

Dosimetry analysis predicts that the dose-limiting organ will be the kidneys. The calculations show that the kidneys receive a mean absorbed radiation dose of 34.9 ± 2 mGy/mCi (or 0.94 ± 0.05 mGy/MBq) in male subjects (the most sensitive sex) when Vamin® 18 Electrolyte Free, an amino acid solution, is administered. The absorbed dose limit for the kidneys is 23 Gy.¹¹ Above this level, radiotoxicity could occur. As a result, it is estimated that significant kidney toxicity is unlikely to occur at levels up to 659 mCi (24.1 GBq) of CAM-H2. For the highest intended dose of 2×200 mCi, the estimated kidney dose is 14 Gy.

Red bone marrow is the most radiosensitive tissue in the body. CAM-H2 results in a red bone marrow exposure of 2.2 ± 0.5 mGy/mCi (or 0.059 ± 0.001 mGy/MBq) in male subjects, based on modeling. The absorbed dose limit for bone marrow is 2 Gy.¹¹ Above this level, significant hematotoxicity is expected. This level of irradiation would only occur at 909 mCi (33.6 GBq) of CAM-H2 in a single dose. Therefore, severe hematotoxicity is unlikely to occur at the doses of CAM-H2 in the current study (100 to 400 mCi). CAM-H2 at a therapeutic cumulative dose of 400 mCi (14.8 GBq) would deliver 0.88 Gy to the red bone marrow.

The dosimetry data for CAM-H2 indicate that CAM-H2 is unlikely to present clinically relevant radiotoxicity to healthy tissues up to the level of 14.8 GBq (2×200 mCi) administered in 1 cycle.

In order to mitigate the risk of kidney radiation injury, an amino acid infusion consisting of arginine and lysine will be administered from 30 minutes before study drug administration to 3 hours after study drug administration, a method routinely used in targeted radionuclide therapy (eg, Lutathera® [Novartis]). Preclinical studies with CAM-H2 show that infusion of arginine and lysine reduces kidney retention levels by approximately 40%.

See Section 7 of the Investigator's Brochure for a detailed description of the justifications.

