- Administer saline 0.9% infusion, starting 30 minutes prior to study drug administration and continuing for up to 3 hours after, at a rate of 200 to 300 mL/hour;
- Administer an amino acid solution beginning 30 minutes prior to study drug administration and ending 3 hours after study drug administration, at a rate of 250 to 500 mL/hour;
- Administer study drug via slow IV infusion, ie, administer using a shielded infusion device over approximately 3 to 30 minutes, depending on the volume to be injected; and
- Perform a planar WB scan and SPECT/CT scan at 5 (± 1) hours, 24 (± 4) hours, and 48 (± 4) hours after study drug administration.

Note: The planar WB scan done at 5 hours will also serve as the PD distribution scan.

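### Some permitted amino acid volumes cannot be given in full at any permitted rate within the stated window, and the line-access instructions conflict

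*Combined protocol and SAP*

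**What the plan says.** **Rate and window.** Section 5.2.5.4 states: "Administration of the amino acid solution should be initiated 30 minutes prior to study drug administration with an infusion rate of 250 to 500 mL/hour". It goes on: "Amino acid solution infusion should be continued for 3 hours after study drug administration". The dosimetry rationale (Section 1.3.2) gives the same window: the infusion "will be administered from 30 minutes before study drug administration to 3 hours after study drug administration". The visit procedures keep the same range of rates and word the end as fixed, for example in Section 6.2.2.1: "Administer an amino acid solution beginning 30 minutes prior to study drug administration and ending 3 hours after study drug administration, at a rate of".

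**Products.** Table 5 describes a compounded bag with 25 g lysine and 25 g arginine in 1 L. Table 6 permits commercial solutions with 18 to 24 g of each amino acid in 1.5 to 2.2 L. The text prefers the compounded bag, partly for its smaller volume. For the alternative it adds: "Rates lower than 320 mL/hour are not recommended for commercial solutions". The Appendix A footnotes repeat that minimum for commercial solutions but describe only the compounded product.

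**Line access.** Section 5.2.2.1 says: "CAM-H2 should always be infused through an IV catheter placed exclusively for its infusion". Section 5.2.2 makes two peripheral lines the default but allows one peripheral catheter, in which case "the amino acid infusion needs to be temporarily halted during the study CAM-H2 infusion and resumed once the catheter has been flushed". Section 5.2.5.4 allows a 3-way stopcock for amino acids, study drug and saline when venous access is poor.

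**Use of kidney dose.** Section 3.1.4.1 makes a kidney dose above 23 Gy a DLT. Further cycles require the cumulative kidney dose to stay below 23 Gy, based on Cycle 1 dosimetry in escalation (Section 3.1.1.2) and on escalation-phase Cycle 1 dosimetry in expansion (Section 3.1.2.2).

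**The concern.** The kidney is the predicted dose-limiting organ, and the amino acid infusion is there to protect it. Section 1.3.2 reports from preclinical work that "infusion of arginine and lysine reduces kidney retention levels by approximately 40" percent, and its 34.9 mGy/mCi kidney coefficient was obtained with a named amino acid product. If rate, volume and stop time cannot all be met, sites must choose which instruction to drop. The protocol does not say which, does not say whether a second compounded bag is hung, and sets no minimum amount to be delivered.

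The 23 Gy rule is therefore exposed wherever kidney dose is projected and not measured again. Escalation Cycles 2 to 4 have no SPECT/CT and one planar scan per dose (Table 1). Expansion images uptake only at 24 h (Table 2) and applies escalation dosimetry to different patients, at 10 to 15 sites against 4 to 8 in escalation. If the infusion delivered differs between the setting where dose was measured and the setting where it is applied, the projection carries an error that nobody can see. Section 5.2.3 requires the time and dose of study drug. Section 5.3.3 requires medications in general. Neither asks for amino acid volume or interruptions.

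**Working it through.** **The plan's own figures.** 400 mCi × 34.9 mGy/mCi = 13.96 Gy (stated: 14 Gy). 23 Gy ÷ 0.0349 Gy/mCi = 659 mCi (stated: 659 mCi). Both reproduce. The plan states no delivered amino acid volume or mass to check.

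**Window.** 0.5 h before plus 3 h after = 3.5 h. If the 3 hours are counted from the end of a 30-minute study drug infusion, the window is 4.0 h.

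**Volume delivered = rate × window.**
- 3.5 h: 250 × 3.5 = 875 mL; 320 × 3.5 = 1120 mL; 500 × 3.5 = 1750 mL.
- 4.0 h: 1000, 1280 and 2000 mL.

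**Rate needed = volume ÷ window.**

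| Volume | 3.5 h | 4.0 h |
|---|---|---|
| 1.0 L compounded | 286 mL/h | 250 mL/h |
| 1.5 L commercial | 429 mL/h | 375 mL/h |
| 1.75 L commercial | 500 mL/h | 438 mL/h |
| 2.0 L commercial | 571 mL/h | 500 mL/h |
| 2.2 L commercial | 629 mL/h | 550 mL/h |

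Against a 500 mL/h maximum, commercial volumes above 1.75 L do not fit in 3.5 h, and volumes above 2.0 L do not fit in 4.0 h.

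**At the 320 mL/h recommended minimum, 3.5 h.** 1120/1500 = 75% and 1120/2200 = 51%. No permitted commercial volume is completed. In 4.0 h the fractions are 1280/1500 = 85% and 1280/2200 = 58%, so none is completed there either.

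**Compounded bag.** At 500 mL/h, 1000/500 = 2 h: the bag is empty 1.5 h after dosing, not 3 h. At 250 mL/h, 875/1000 = 87.5% is in at 3.5 h, or 25 × 0.875 = 21.9 g of each amino acid.

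**Grams of each amino acid if the infusion stops at 3 h after dosing.**
- Low end: 18 g in 2.2 L at 320 mL/h: 18 × 1120/2200 = 9.2 g.
- One full compounded bag: 25 g. Ratio 25/9.2 = 2.7.
- In the 4.0 h window: 18 × 1280/2200 = 10.5 g; ratio 2.4.
- The 320 mL/h figure is only a recommendation. At 250 mL/h: 18 × 875/2200 = 7.2 g; ratio 3.5.

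**If every bag is completed instead.** 25/18 = 1.4-fold, but 2.2 L then takes 2200/500 = 4.4 h at the maximum rate, past the stated end.

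**Limit on the kidney effect.** If the 40% preclinical reduction applies to absorbed dose, no protection against full protection is 1/(1 − 0.4) = 1.67-fold. As an illustration of how much room the rule leaves, two cycles at Level 3 total 2 × 2 × 150 = 600 mCi, which projects 600 × 0.0349 = 20.9 Gy; 23/20.9 = 1.10, so a kidney dose 10% higher reaches the limit.

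**Line access.** One section requires an exclusive catheter for study drug without exception; two others allow shared access. The halt required with a single catheter falls on the study drug infusion itself, normally about 3 to 30 minutes. A 30-minute halt takes 0.5 h from either window.

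**The case against.** The case on the other side has real force.

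- **Much of the range works.** The preferred 1 L bag fits at about 286 mL/h (250 mL/h in a 4 h window), and commercial 1.5 to 1.75 L fits at 429 to 500 mL/h. At 500 mL/h the compounded bag still delivers its full 25 g, only sooner. This stands: the instructions are not incompatible throughout.
- **The low end is a corner case.** The 9.2 g figure combines the lowest content, the largest volume, the lowest recommended rate and a stop with fluid left. That is fair, but each element is permitted, and the visit procedures do fix the end time. A higher extreme of 43.8 g (25 × 1.75) needs a second compounded bag, which no section mentions, so it is not used here.
- **Grams are not protection.** A reader might infer that kidney protection differs severalfold between compliant patients. The documents give no relation between amount delivered and protection, and their one figure caps the kidney-dose difference at about 1.67-fold.
- **Crossing 23 Gy in one cycle.** A reader might apply that cap at 2 × 200 mCi: 13.96/0.6 = 23.3 Gy. That assumes no amino acids at all, which no permitted regimen amounts to, and Level 4 is optional. If protection were proportional to grams up to 25 g (an assumption), 9.2 g would give 23.27 × (1 − 0.4 × 9.16/25) = 19.9 Gy.
- **The escalation DLT is measured.** Scans at 5, 24, 48 and 168 h after each Cycle 1 dose reflect the infusion actually given. This stands, and confines the exposure to later cycles and expansion.
- **Shared access is a fallback.** True, but the exclusive-catheter sentence makes no exception for it. The kidney effect of the halt is not quantified.

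**Conclusion.** The concern holds as a partial contradiction. Commercial volumes above 1.75 L (above 2.0 L on the 4 h reading) cannot be given in full at any permitted rate inside the stated window, the 320 mL/h minimum completes no permitted commercial volume, and a single compounded bag at the top rate runs out before the stated end. These results need only the protocol's own figures. The line-access statements cannot all be followed either.

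The size is about 2.7-fold in grams of each amino acid between patients who follow the text, if the infusion stops at 3 h and the recommended minimum is respected, or 1.4-fold if every bag is completed. What this does to kidney dose cannot be read from the documents. The 1.67-fold cap rests on two assumptions: that a preclinical retention figure carries over to absorbed dose in patients, and that the 34.9 mGy/mCi coefficient represents full protection.

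The documents do not support the inference that the escalation Cycle 1 kidney DLT is unreliable, or that a compliant patient would exceed 23 Gy in one cycle because of the infusion. The weak points are later escalation cycles given with a different solution or rate, and expansion, where dosimetry from other patients is carried over.

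**What to change.** The sponsor must reconcile the rate, volume and end-time statements in Section 5.2.5.4 with Tables 5 and 6, state whether volume or end time governs, and reconcile the line-access statements in Sections 5.2.2, 5.2.2.1 and 5.2.5.4. The result should be carried into Sections 6.2 and 6.3 and the Appendix A footnotes. The choice of regimen and access rule belongs to the protocol team; none is proposed here.

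For each dose, record the solution used, start and stop times, interruptions and volume delivered. Before escalation dosimetry is applied to expansion patients, describe kidney absorbed dose per mCi by solution and amount delivered.

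The cost is amendment wording, a few eCRF fields and one descriptive table. With at most 18 escalation patients over up to four dose levels, that table will be sparse: it can show whether practice varied, but it cannot estimate a dose-response for protection.
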